Further, COT has substantial potential for harm. Opioid overdose deaths continue to be an "epidemic," with over 46,000 deaths in 2018. Men have almost twice the mortality rate from opioid use than women. In one study, most prescription opioid overdose deaths were attributed to diversion, illustrating that opioid risks are not limited to individuals receiving opioid prescriptions. Additionally, individuals on higher doses of COT are at greater risk for overdose death and for the development of misuse or abuse. The annual societal cost of opioid abuse was estimated at \$55.7 billion in 2007. In younger persons, new marijuana use and new misuse of prescription opioids are roughly equivalent. Other substantial unintended consequences include opioid-induced decreases in quality of life. The Centers for Disease Control and Prevention (CDC), the Federation of State Medical Boards, and individual state medical boards have issued guidelines to promote the safe and effective prescribing

of opioid analgesics. These guidelines advise that opioids only be used when other pharmacological and nonpharmacological treatment modalities are not effective. Clinical guidelines for opioid prescribing emphasize patient selection for opioid initiation, monitoring, and reducing opioid misuse and abuse. However, the guidelines and scientific literature generally provide only limited discussion of opioid reduction or discontinuation if an opioid-based approach is not working for the patient. That is, guidelines address only the technical aspects of reducing medication dosages for COT (i.e., how quickly to decrease the dosage). Importantly, the existing literature does not discuss how to motivate individuals to discontinue or decrease their opioid dosage or to reduce the risk of opioid misuse; nor how to manage pain symptoms in a patient-centered fashion during and after opioid reduction or discontinuation. This evidence gap leads to a predictable clinical practice gap. In the absence of an evidence base to guide providers and patients on how to decrease opioids, reduction in opioid dosage or discontinuation of COT is infrequent.

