**Table 6. Schedule of Assessments**

Measurement	Screening (Month -12 to 0)	Enrollment/ Baseline Survey (Month 0)	Baseline Clinical Data Extraction (Month -3 to 0)	Intervention visits (Months 1-12)	Clinical Data Extraction (Months 6, 12, 18)	T2 follow-up survey (Month 6)	T3 follow-up survey (Month 12)	Qualitative research activities
Informed consent	•							•
Demographics		•	•					
Randomization		•						
Average daily opioid dose			•		•			
Charlson Comorbidity Index (ICD-9/10)			•					
Chronic noncancer pain conditions (ICD-9/10)			•					
Mental health disorders (ICD-9/10)			•					
Alcohol/substance use disorders (ICD-9/10)			•					
Body mass index (based on height and weight)			•					
Health insurance payer		•	•		•			
Opioid withdrawal or overdose medication prescriptions			•		•			
Study intervention intensity (based on number of intervention visits)					•			
PROMIS self-report scales: (Pain Interference, Physical functioning, Pain Intensity, Anxiety, Depression)		•				•	•	
Brief Pain Inventory (11 key items)		•				•	•	
Health literacy level		•						
Patient centered communication		•				•	•	•
Self-reported relative opioid use						•	•	
Intent to taper		•				•	•	•
Use of intervention content						•	•	•
Satisfaction with care		•				•	•	•
Adverse Events and death review and evaluation			•	•	•	•	•	
Fidelity review and evaluation				•		•	•	

Cross-reference: UNC IRBIS Application section A.9.1 (identifiers).

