#### 8.1.5 Potential Physical Risks

*Cross-reference: UNC IRBIS Application section A.6.9, A.6.10.*

There is some potential risk that participants may experience increased pain if they reduce or discontinue their opioid medication.

We expect any side effects to be rare or infrequent and mild-to-moderate.

This study is comparing two different behavioral interventions for patients with chronic pain who are already on chronic opioid therapy. Some of the intervention content is about tapering or discontinuing opioids. The participant may choose to request to taper or discontinue opioids. Lowering the dose of opioids has the potential for side effects from withdrawal. But, there are no extra risks from this study compared to discontinuation as part of usual care.

The approach of this trial is to promote a controlled opioid reduction, which in some cases might lead to complete discontinuation, with a patient's consent. The protocol does not specify or foresee abrupt tapering.

If patients do choose to taper, the physicians will be doing a very gradual taper of their opioids (as per CDC guidelines, 10% per week), which has rare to infrequent risk of withdrawal. If withdrawal is experienced, mild to moderate symptoms are expected. These symptoms may include low energy; irritability; anxiety; agitation; insomnia; sweats; muscle aches and pain; as well as abdominal cramping, nausea, and vomiting. Patients will be advised to call their provider if they experience symptoms of withdrawal.

To reduce physiological risk, certain safeguards will be implemented at RTI and at all clinical institutions. Procedures to reduce clinical risk include intensive medical monitoring of AEs and medical management common for this study population.

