**Table 11. Reportable Events and Assessment Methods**

Reportable Event	Assessment Method
Suicide risk (active suicidal ideation or attempted suicide) (see section 8.3.5 below)	Adverse Event Case Report Form
All Deaths (including opioid-related, suicide, and all other deaths)	Adverse Event Case Report Form, PCORnet EHR-based data, National Death Index (available after study completion), publicly available data
Hospitalizations or Emergency Department (ED) visits related to opioid use (overdose or withdrawal) or related to suicide attempt	Adverse Event Case Report Form, PCORnet EHR-based data, patient self-report via 6- and 12-month follow-up surveys

When one of these AEs is identified, the institution PI or designee will assess the event to evaluate whether it is one of the following:

- Unanticipated (i.e., unexpected). These events are AEs that are new or greater than previously known, in terms of nature, severity, frequency or occurrence, as documented in the protocol, consent, or other study documents approved by the IRB (OHRP-  
<https://www.hhs.gov/ohrp/regulations-and-policy/guidance/reviewing-unanticipated-problems/index.html>).
- Related (possibly related, probably related, or definitely related) to study participation.

Institutions will record all reportable events in REDCap in the Adverse Event Case Report Form.

Reporting will either follow an expedited or periodic timeline.

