4.7 Study Flow Chart of Assessments and Evaluations

Measurement	Screening (Month -12 to 0)	Baseline Survey (Month 0)	Baseline CDM Extraction (Month -3 to 0)	Intervention visits (Months 1-12)	CDM Extraction (Months 6, 12, 18)	T2 survey (Month 06)	T3 survey (Month 12)
Informed consent	•						
Demographics	•					•	•
Health literacy level		•					
Randomization		•					
Average daily MED			•		•		
Medical encounters			•		•		
Charlson Comorbidity Index (ICD-9/10)			•		•		
Chronic noncancer pain conditions (ICD-9/10)			•		•		
Mental health diagnoses (ICD-9/10)			•		•		
Alcohol/substance use diagnoses (ICD-9/10)			•		•		
Body mass index (based on height and weight)			•		•		
Health insurance payer			•		•		
Opioid withdrawal medication prescriptions			•		•		
Administer study intervention				•			
EHR template note					•		
Adverse Event Case Report form (as indicated)				•			
Brief Pain Inventory		•				•	•
PROMIS self-report scales: (Pain Interference, Physical functioning, Pain Intensity, Anxiety, Depression)		•				•	•
Current psychotherapy		•				•	•
Self-reported opioid use and intent to taper		•				•	•
Use of intervention content; knowledge check						•	•
Hospitalization or ED visits related to opioid use (overdose or withdrawal) or suicide attempt			•		•	•	•
Death					•		
Adverse Event review and evaluation	•	•	•	•	•	•	•
Fidelity review and evaluation				•		•	•

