Intent to Taper	Ordinal and Binary	
A question on the T1, T2, and T3 survey includes:
 
Please say how much you agree with this statement: "Reducing the amount of opioid medicines I take is a goal of mine" with response options including Strongly Agree, Agree, Uncertain, Disagree, and Strongly Disagree.
 
In addition to reporting the frequency of initial response options, responses of Strongly Agree and Agree will be re-classified as an intent to taper, while Uncertain, Disagree, and Strongly Disagree will be re-classified as no intent to taper.

Relative opioid use self-report (from T3 survey)	Ordinal	A question on the T2, and T3 survey includes my overall use of opioids has increased, stayed the same, decreased.
Safety Outcomes		
Adverse Events (AEs); 1) Opioid Withdrawal Overdose, 2) Suicidality Risk, and 3) Death	Count and proportion	Three different types of AEs will be collected throughout the intervention phase of the study (from randomization to 12-months post-randomization): 1) opioid withdrawal or overdose, 2) suicidality risk, and 3) death. AEs will be identified and reported from the REDCap study database, the 6 and 12-month follow-up surveys, and deaths from the electronic medical records (based on ICD-10 codes). To identify duplicate AE reporting and corroborate AE details, we collect AE type and onset date in each database. If the same AE is reported in multiple different databases, it will only be counted as one AE. The total number of AEs as well as any documented AE will be examined.
Subgroups and Other Covariates		

Variable	Type	Definition
Mental Health Disorder Flag(s)	Binary	
Includes an indicator for any mental health disorder recorded as a diagnosis in the EHR, as well as binary indicators for the presence in the EHR of each of the following: adjustment disorder, anxiety, ADHD, dementia, developmental disorder, childhood disorders, impulse control disorder, mood disorder, personality disorder, schizophrenia or other psychotic disorder, suicidal ideation, and other miscellaneous mental health disorders.
 
The ICD-10 codes used to identify Mental Health Disorders was pulled from the Healthcare Cost and Utilization Project Agency for Healthcare Research and Quality (H-CUP-AHRQ) website (https://hcup-us.ahrq.gov/toolssoftware/ccs10/ccs10.jsp#download)

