9.7 Safety and Adverse Events Analysis

AEs will be listed and summarized overall and by event term (hospitalization or emergency department visit due to opioid withdraw/overdose, suicidality, and death). The number and proportion of individuals experiencing an adverse event, any SAE, and AE by relationship to intervention will also be summarized.

Contingency table methods will be used to generate point and interval estimates of the risk of each AE type by intervention arm. Treatment groups will be compared using an unadjusted chi-squared test. Event rates are too small to stratify by clinical site. For events with expected cell counts < 5, groups will be compared with a Fisher's exact test, where specified, Binomial 95% CIs for proportions are based on the exact Clopper-Pearson method (ref Clopper, Pearson).

In SAS, using PROC FREQ:

The chi-square test and corresponding risk difference 95% CI are obtained by:

```
table Intervention *AEvar /riskdiff(method=wald equal var=null) chisq ;
```

For small expected cell counts, the exact test and risk difference 95% CI are obtained by:

```
table Intervention*AEvar / fisher; exact riskdiff (method=score);
```

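### Hospital and ED visits for opioid withdrawal and for overdose are compared between arms only as one pooled event type; report them on separate rows and state that milder withdrawal is not captured

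*SAP*

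**What the plan says.** SAP 9.2 (Safety Outcomes) defines three adverse event types, collected from randomization to 12 months: "1) opioid withdrawal or overdose, 2) suicidality risk, and 3) death". SAP 9.7 summarises them by event term and gives the terms as "hospitalization or emergency department visit due to opioid withdraw/overdose, suicidality, and death". Each type is compared between arms with an unadjusted chi-squared test, or Fisher's exact test when expected counts are below 5. Clopper-Pearson limits are available for the proportions.

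The joint term comes from the protocol. Table 11 has one reportable row, "Hospitalizations or Emergency Department (ED) visits related to opioid use (overdose or withdrawal) or related to suicide attempt". Protocol 5.2.3 limits safety outcomes to serious events, and 8.3.1 says that serious events off the list are not recorded.

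On how each harm relates to dose:
- Protocol 8.1.5 says that lowering the dose can cause withdrawal, rarely to infrequently with a gradual taper, and adds: "If withdrawal is experienced, mild to moderate symptoms are expected".
- Protocol 1.1 says that "individuals on higher doses of COT are at greater risk for overdose death".
- Protocol 8.3 expects the trial's adverse events to take the form of effects of reducing the opioid dose.

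Both schedules also list prescription data: "Opioid withdrawal or overdose medication prescriptions" in protocol Table 6 and "Opioid withdrawal medication prescriptions" in SAP 4.7, at baseline and months 6, 12 and 18. SAP 9.2 and 9.7 define no outcome from them.

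**The concern.** The primary question is which arm lowers opioid dose more. The natural balancing question is whether that arm also has more withdrawal. The planned safety comparison cannot answer this, because withdrawal visits are always added to overdose visits before the arms are compared.

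The two harms have different links to dose in the protocol. If the arm with the larger dose reduction had more withdrawal visits and fewer overdose visits, the pooled rates could look alike. If overdose did not differ at all, it would still add noise to a withdrawal difference. Either way, a pooled result of no difference supports no statement about withdrawal, and none about overdose.

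There is also a limit of coverage. The protocol expects withdrawal to be mild to moderate, but the safety table holds only withdrawal that led to a hospital or ED visit. A reader of the results could take a low count to mean little withdrawal.

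**Working it through.** **Step 1. Is a separate comparison specified anywhere?** SAP 9.2 has one joint type, SAP 9.7 one joint term and protocol Table 11 one joint row. No section of either document compares withdrawal or overdose alone by arm.

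**Step 2. Inputs.** The documents state no rate, sample size or power for either event, so there is no plan figure to reproduce. SAP 6 gives 526 randomized; at 1:1 that is 526 / 2 = 263 per arm. Every event rate and count below is an assumption.

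**Step 3. What pooling does to power.** Two-sided 0.05, n = 263 per arm, p̄ = (p1 + p2)/2:

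power = Φ[(|p1 − p2| − 1.96·√(2p̄(1 − p̄)/n)) / √((p1(1 − p1) + p2(1 − p2))/n)]

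For withdrawal alone at 4% vs 1%, p̄ = 0.025, the null standard error is 0.01362 and the alternative 0.01355. So power = Φ[(0.03 − 0.02669)/0.01355] = Φ(0.24) = 60%.

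Now add overdose, assuming that no participant has both events:

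| Overdose, same arm order | Pooled rates | Power of pooled test |
|---|---|---|
| 1% vs 4% | 5% vs 5% | no difference left to detect |
| 1% vs 3% | 5% vs 4% | 8% |
| 1% vs 2% | 5% vs 3% | 21% |
| 2% vs 2% | 6% vs 3% | 38% |
| 2% vs 1% | 6% vs 2% | 65% |

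Full cancellation needs equal and opposite effects. Dilution needs only that overdose does not differ. When both effects run the same way, pooling slightly helps (65% against 60%).

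**Step 4. The extreme case in counts.** Suppose withdrawal is 10 vs 3 and overdose 3 vs 10. Alone, each is 10/263 = 3.8% vs 3/263 = 1.1%. Expected counts are (10 + 3)/2 = 6.5 per arm, so SAP 9.7 selects the chi-squared test: p = 0.049 (Fisher p = 0.088). Clopper-Pearson limits are 1.8% to 6.9% and 0.2% to 3.3%. Pooled, the counts are 13 vs 13, risk difference 0, p = 1.0. This mirror image was chosen to show that cancellation is possible. It is not a forecast.

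**Step 5. What the hospital/ED limit leaves out.** Suppose any withdrawal occurs in 20% vs 10%. Counting all of it gives 90% power. If only 25%, 10% or 5% of cases reach a hospital or ED, power falls to 33%, 15% or 10%. The documents give no such share. The point is only that a count of visits says little about withdrawal overall.

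**The case against.** The strongest reply has five parts.

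- **The opposite direction is inferred.** The line in protocol 1.1 concerns overdose death, and death is already its own event type. The protocol does not say that dose reduction in this trial lowers non-fatal overdose visits. This stands: the documents support only that the two harms need not move together.
- **Events will be few.** Protocol 5.3.2 expects adverse events to be relatively rare, and SAP 9.7 calls the rates too small to stratify by site. SAP 7.6 treats these comparisons as descriptive. This stands too. It weakens any test, but not the case for showing the two counts apart.
- **Nothing is irretrievably hidden.** SAP 9.7 also lists the events, so recorded visits might be sorted by hand. SAP 11 places the table shells in a separate file and lets displays be added without amendment, so the shells may already split the term. But a listing is not a pre-specified comparison by arm.
- **The hospital/ED limit is a declared design choice.** Protocol 5.2.3 and 8.3 adopt a short list for a pragmatic trial, and no SAP edit can recover symptoms that were never collected. This stands, so the remedy is a statement of the limit.
- **Related harms are analysed.** SAP 9.6.6 tabulates worsening pain interference or function with a dose decrease, and SAP 9.6.1 compares anxiety and the Brief Pain Inventory scores by arm. These bear on the harms of dose reduction, but do not count withdrawal.

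Two stronger readings are tempting. A reader might infer that the pooled rate will cancel a real effect. With no rates and no stated direction for overdose visits, the documents show only that it could. A reader might also infer that the scheduled withdrawal-medication data already supply a ready outcome for milder withdrawal. They do not. No drug list is given, and protocol Table 6 mixes in overdose medications. The fields in protocol 4.1.4 include no indication by which preventive naloxone (6.1) could be removed. Month 18 lies beyond the 12-month adverse event window and, by SAP 4.6, is likely incomplete for the last participants.

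**Conclusion.** The point holds as a reporting gap in the safety analysis. The plan compares only the pooled withdrawal-or-overdose visit rate, so a result of no difference cannot be read as evidence about either harm. On the assumed rates, a withdrawal difference detectable with 60% power alone falls to 38% when overdose is equal between arms, and to 8% or nothing when overdose runs the other way. It is not masked when both run the same way. These sizes rest wholly on assumed rates, 263 per arm and no participant with both events.

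The safety table also does not measure the mild-to-moderate withdrawal that the protocol expects. That follows from the protocol's design and should be stated beside the results. No primary or key secondary conclusion changes.

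**What to change.** In SAP 9.2 and 9.7:

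1. Classify each event of the first type as withdrawal, overdose or unclassifiable, using the adverse event form, the 6- and 12-month surveys and the ICD-10 data. SAP 9.2 can be read as using the health record for deaths only, so name the ICD-10 extraction of SAP 4.4.1 as a source here.
2. Report withdrawal visits and overdose visits as separate rows by arm, with exact confidence intervals. Keep the pooled row, which also holds the unclassifiable events.
3. State in the safety section that withdrawal not leading to a hospital or ED visit is not captured, so the table does not measure the mild-to-moderate form.

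Optional and supportive only: a descriptive summary by arm of the withdrawal-medication prescriptions already extracted, with a pre-specified drug list that excludes naloxone and a 12-month window matching the adverse event window. Some such drugs may have other uses, so this cannot stand in for a withdrawal count.

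The cost is a few lines of SAP text, a classification step and two table rows; the required changes need no new data collection. The downside is small counts per row. The form and survey items are not among the documents, so some events may prove inseparable, and the retained pooled row covers them.

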### 8.3.5 Suicidality

We will capture suicide risk (active suicidal ideation or attempted suicide) during the intervention period during clinical encounters. As this is a pragmatic unmasked behavioral intervention trial, suicide risk will only be captured if the participant indicates intent to self-harm during the clinical intervention visit; the provider will not conduct a study-specific suicide risk assessment. If the clinic becomes aware of suicide ideation, the provider will follow the institution's or clinic's protocols, as described in our **Safety Protocol** (see Appendix). Similarly, if active suicide ideation is self-reported to the research coordinator during the screening visit review of exclusion criteria, the provider will be notified and will follow the institution's or clinic's protocols.

The therapists delivering the MI +CBT-CP intervention will all be masters- or PhD-level mental health providers with training and experience handling suicidal patients. If a participant does express suicidal ideation, the therapist will handle it in the manner that they would in their clinical practice. Similarly, if a participant being seen in the SDM intervention (Arm 1) expresses suicidal ideation, the clinic will handle it in the manner that they would in their clinical practice.

The provider will report the event to the institution's Research Coordinator, and the Research Coordinator will complete an Adverse Event Case Report Form.

We will capture whether the participant has been to the ED or had an inpatient hospitalization because of self-harm via self-report and PCORNet CDM data extraction. We will capture information on when and where this occurred.

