4.4 Electronic Health Record (HER) Data in the CDM

4.4.1 Data Stored in the CDM

The EHR data extracted from the CDM contains the study's primary outcome (average daily opioid dose in MED), which is derived from each participant's prescription data. This data source also contains important subgroup variables including vital signs and CNCP, and substance use and mental health diagnoses. The study will also be extracting potential adverse events based on ICD-10 codes and insurance provider information. Each site will also perform a separate 'sidecar' request to pull out the total number of SDM visits per participant (based on attendance at a healthcare visit with a trained SDM provider, clinic notes and smartphrases), including the delivery mode of the visit (in-person vs. telehealth). A sidecar request is necessary for this type of data since this data is not included in the CDM.

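### SAP 9.2 names the EHR as an adverse-event source for deaths only and stops counting at month 12, an unflagged conflict with the protocol and with SAP 4.4.1 and 4.7

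*SAP*

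**What the plan says.** SAP 9.2, in the Safety Outcomes row, defines three adverse-event types: opioid withdrawal or overdose, suicidality risk, and death. On timing: "Three different types of AEs will be collected throughout the intervention phase of the study (from randomization to 12-months post-randomization". On sources: "AEs will be identified and reported from the REDCap study database, the 6 and 12-month follow-up surveys, and deaths from the electronic medical records". Duplicates across databases are removed by event type and onset date. SAP 9.7 then tabulates hospital or ED visits for withdrawal or overdose, suicidality, and death, but names neither a source nor a window, so the 9.2 definition governs.

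Other parts of the two documents are wider:

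- Protocol Table 11 lists as reportable "Hospitalizations or Emergency Department (ED) visits related to opioid use (overdose or withdrawal) or related to suicide attempt", with these sources: "Adverse Event Case Report Form, PCORnet EHR-based data, patient self-report via 6- and 12-month follow-up surveys".
- Protocol 8.3.5 adds: "We will capture whether the participant has been to the ED or had an inpatient hospitalization because of self-harm via self-report and PCORNet CDM data".
- Protocol Table 6 marks adverse-event and death review under the clinical data extractions at months 6, 12 and 18.
- SAP 4.7 marks the row "Hospitalization or ED visits related to opioid use (overdose or withdrawal) or suicide attempt" under the CDM extractions at months 6, 12 and 18, and marks the death row there too.
- SAP 4.4.1 says: "The study will also be extracting potential adverse events based on ICD-10 codes".

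**The concern.** The trial tries to lower opioid dose and reports dose to month 18, a key secondary timepoint. Overdose, withdrawal and self-harm are the harms a reader will look for beside that result. If the safety tables follow 9.2 literally, an 18-month dose change is reported with no harms counted for its last six months.

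Within the first 12 months, non-fatal events would be known from site forms and surveys. SAP section 6 puts survey completion at about 60%. SAP 8.1 says that many participants may have completed no intervention visit and could not be reached by coordinators, yet still have EHR extractions. For such a person who also returned no survey, the EHR is the most reliable source left.

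Contact also differs by arm. The protocol expects 4 to 12 SDM visits over about 12 months. In the other arm it expects one MI session and up to eight CBT sessions, possibly all within three months. Form reporting prompted by intervention visits could therefore differ by arm, whereas EHR capture does not depend on study contact.

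**Working it through.** The plan gives no adverse-event rate or count, so there is no figure to reproduce. The check is mainly a comparison of texts.

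**Sources and window, side by side**

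| Place | EHR used for non-fatal hospital/ED events? | Time |
|---|---|---|
| SAP 9.2 | Not named; EHR named for deaths | Randomization to month 12 |
| SAP 9.7 | No source given | No window given |
| SAP 4.4.1 | Yes, potential events by ICD-10 code | Not stated |
| SAP 4.7 | Yes | Extractions at months 6, 12, 18 |
| Protocol Table 11 | Yes | No 12-month limit |
| Protocol 8.3.5 | Yes, for self-harm | No 12-month limit on this item |
| Protocol Table 6 | Adverse-event and death review at the extractions | Months 6, 12, 18 |

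The SAP openly records other departures from the protocol: the time intervals (9.2, 9.3), the random subject effect (9.3) and time to discontinuation (9.6.3). It records none here.

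**Window.** Dose follow-up is 18 months and event counting is 12 months. (18 - 12)/18 = 6/18 = 33% of the window is uncounted. This is a share of time, not of events.

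**Illustration of what that time could hold.** N = 526 randomized (SAP section 6). The rates r are assumptions: the documents say only that events should be relatively rare. With a constant rate and full follow-up, expected events are 526 × r × years, and the chance of at least one event in months 12-18 is 1 - exp(-526 × r × 0.5).

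| Assumed r per person-year | Expected, 0-12 months | Expected, 0-18 months | Uncounted | Chance of at least one uncounted |
|---|---|---|---|---|
| 0.5% | 2.6 | 3.9 | 1.3 | 73% |
| 1% | 5.3 | 7.9 | 2.6 | 93% |
| 2% | 10.5 | 15.8 | 5.3 | over 99% |
| 5% | 26.3 | 39.5 | 13.2 | over 99% |

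These are upper figures for each rate. SAP 4.6 says the last participant will probably lack 18 months of EHR data, and SAP section 6 gives 20% discontinuation.

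**Survey reach.** If 40% miss each survey, the share missing both lies between max(0, 0.40 + 0.40 - 1) = 0 and 0.40. The ceiling is 526 × 0.40 = about 210 participants; the actual share is not stated.

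**Months 0-12, illustration.** Suppose surveys reach 60% of events, responders report every event, and non-response is unrelated to events. Let c be the share of the remaining events that the REDCap form catches. The share found is 1 - (1 - 0.60)(1 - c): 60% at c = 0, 80% at c = 0.5, and 96% at c = 0.9. The value of c is unknown.

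**The case against.** The strongest reply is that EHR-found events may reach the tables through REDCap. Protocol 8.3.1 has institutions enter every reportable event in REDCap, and protocol 8.2.2 describes the REDCap adverse-event data as available from the CDM extraction or surveys. This stands in part, and it is why a reader should not infer that non-fatal EHR events **will** be lost; they **can** be. It does not close the gap. SAP 9.2 lists EHR deaths apart from REDCap and removes duplicates across databases, so it treats them as separate feeds. SAP 4.6 locks REDCap after the last participant's 12-month phase and query resolution, while the final extraction is planned for July or August 2023. No lock date is given, but the lock could come first.

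Second, the 9.2 sentence may be loose drafting. It ties ICD-10 codes to deaths, whereas protocol 4.1.4 describes death data as date and source; that suggests a wider pull was meant. This is plausible, and then a short clarification settles the source question.

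Third, a mark in an extraction column need not define a counting window. SAP 4.7 marks BMI and chronic pain diagnoses in the same column, although SAP 9.2 takes both from around or before randomization. That weakens the inference from SAP 4.7 alone. It does not work for protocol Table 6, which marks those two rows at baseline only but adverse events at months 6, 12 and 18. It is fair that no protocol safety passage states an 18-month window in words, and that protocol 8.3.5 limits suicide risk voiced at clinical encounters to the intervention period. The month-18 point therefore covers only EHR-derived hospital/ED events and deaths.

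Fourth, safety comparisons are descriptive, and ICD-10 hits are only potential events: protocol 8.3.1 requires a site assessment of expectedness and relatedness. Both points stand, and the second bears on the fix.

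**Conclusion.** The conflict is real, both between SAP and protocol and inside the SAP. Two consequences follow if 9.2 is applied as written:

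- Events in months 12-18, one third of the dose window, are not counted. This follows from the text; there is no loss only if no such event occurs.
- Non-fatal hospital/ED events found only in the EHR can be missed in months 0-12, unless sites also entered them in REDCap.

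The size of the undercount cannot be derived. Two stronger readings are tempting and unsupported. One is that a third of events are lost: 33% is time, and no event rate is given. The other is that 40% of participants have the site form as their only source: 40% is a survey-level missing rate and only a ceiling on the share returning neither survey, and it ignores the REDCap route for EHR-found events. The event counts in the illustration rest wholly on assumed rates.

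**What to change.** Amend SAP 9.2 so that it:

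- names EHR (ICD-10) hospital/ED events for opioid overdose, withdrawal or suicide attempt as a source, alongside the adverse-event form, the two surveys and EHR deaths;
- reports months 0-12, and separately reports EHR-derived hospital/ED events and deaths to month 18 or the last available EHR date;
- leaves suicide risk voiced at clinical encounters limited to the intervention period, as in protocol 8.3.5;
- keeps the existing removal of duplicates by type and onset date;
- labels as unassessed any EHR-only event without the site assessment of expectedness and relatedness.

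If the narrower definition is deliberate, say so as a change from the protocol, with the reason. The extraction is already planned, so the cost is SAP wording, some programming, and either labelling or site assessment of the EHR-only events.
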